PPH contributes to near-miss cases in addition to actual deaths, due to the serious complications that can occur as a consequence of serious PPH. These include adult respiratory distress syndrome, coagulopathy, shock, loss of fertility, and pituitary necrosis (Sheehan syndrome) (4). If PPH is prevented this could contribute towards reduced hospital stay, avoidance of expensive interventions for intractable PPH (such as hysterectomies and the need for blood products) and conserve our already strained resources.

Prophylactic TXA use has been shown to produce a statistically significant decrease in postpartum blood loss; however, this may not convey clinical significance in terms of transfusion rates and maternal comorbidity from severe haemorrhage. Currently, there is no consensus regarding the optimal timing or dosing of prophylactic TXA for caesarean deliveries (33).

In the light of the above, this research proposes to assess the efficacy of TXA in preventing PPH after caesarean delivery in a population large enough to be adequately powered to add to the current body of evidence. Also, there are no published RCTs, in Southern Africa reporting on TXA in obstetric patients.

GOAL STATEMENT

The aim of this study is to compare the effect of a low dose of TXA (1 g) at the time of skin incision during caesarean delivery together with prophylactic oxytocin administration, versus prophylactic oxytocin alone in an open label randomized clinical trial.

RESEARCH QUESTION

Does intravenous TXA 1g plus Oxytocin 10 IU result in a lower incidence of primary postpartum haemorrhage compared to Oxytocin 10 IU alone after caesarean section?

OBJECTIVES

- 1. To assess the effect of TXA (1g) on postpartum blood loss at caesarean delivery.
- 2. To determine the potential adverse effects of intravenous TXA administered at caesarean section.

PRIMARY OUTCOME

Incidence of PPH, defined by a calculated estimated blood loss > 1000ml or a red blood cell transfusion up to day 2 postpartum

Secondary Outcomes

- Other outcome measures describing postpartum blood loss including
 - o calculated blood loss,
 - visually estimated blood loss,
 - o mean/median number of units of packed red blood cells transfused,
 - o incidence of postpartum shock;
 - o proportion of women requiring supplementary uterotonics,
 - o incidence of postpartum transfusion,
 - o incidence of emergency surgery for PPH including caesarean hysterectomies,

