Preoperative haematocrit will be determined on the day before elective caesarean or on the day of emergency caesarean delivery. Postoperative haematocrit will be the haematocrit obtained by blood sampling at D2 (on the second morning after caesarean section). If haematocrit is not available at D2, then haematocrit at D3 will be considered; if it is also missing, then the postpartum haematocrit closest to D2 in the absence of transfusion will be considered (36,37).

All women who receive RBC transfusion for PPH between delivery and D2 postpartum are defined to have PPH and meet the criteria for the primary outcome. Calculated blood loss is impossible to determine for these women. Moreover, women only rarely receive an RBC transfusion for a blood loss less than 1000 ml. As a marker of significant maternal morbidity, RBC transfusion is considered equivalent or superior to blood loss greater than 1000 mL(25).

Although visual estimation is the method used frequently by anaesthetists to estimate blood loss, it has been demonstrated as inaccurate in repeated studies. The estimate of blood loss is affected by amniotic fluid as well. Its continued use in clinical practice is likely related to tradition and it being easily used. We will also take note of the visual estimate made by the anaesthetist, and by the operating surgeon, as this is the method used locally(6,38)(39)

Secondary outcome measures

Describing postpartum blood loss

1. Clinical

- a. Visually estimated blood loss
- b. proportion of women requiring supplementary uterotonic treatment
- c. incidence of postpartum transfusion
- d. mean number of RBC units transfused
- e. incidence of emergency surgery for PPH including caesarean hysterectomies
- f. incidence of hypovolemic shock related to PPH as determined by assessing BP and pulse
- g. incidence of transfer to ICU
- h. incidence of maternal death from any cause
- i. length of hospital stay.

2. Laboratory

- a. incidence of calculated blood loss > 500 mL and > 1500 mL
- b. mean total calculated blood loss
- c. mean peripartum change in haemoglobin (difference between haemoglobin before delivery and at D2)
- d. Haemoglobin drop > 2 g/dL (between haemoglobin before delivery and at D2) (34).

Describing adverse events

1. Clinical

a. Hemodynamic parameters (heart rate, blood pressure) 15, 30, 45, 60, and 120 min after delivery

- b. the occurrence of potential mild adverse effects of TXA in the operating room:
 - i. nausea
 - ii. vomiting

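### Two primary-outcome rules fail for a small, unknown number of women: a D3 haematocrit taken after a late transfusion is accepted, and an untransfused haemorrhage death before sampling is left unclassified

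*Combined protocol and SAP*

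**What the plan says.** The section Primary Outcome of the combined protocol and SAP defines the endpoint as "Incidence of PPH, defined by a calculated estimated blood loss > 1000ml or a red blood cell transfusion up to day 2 postpartum".

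Under Assessment, Primary outcome measure, calculated loss is estimated blood volume (weight in kg × 85 mL) times the fall in haematocrit divided by the preoperative haematocrit. The postoperative value comes from D2, the second morning after surgery. Two fallbacks follow: "If haematocrit is not available at D2, then haematocrit at D3 will be considered"; and "if it is also missing, then the postpartum haematocrit closest to D2 in the absence of transfusion will be considered".

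The transfusion route is restated there as "All women who receive RBC transfusion for PPH between delivery and D2 postpartum are defined to have PPH". The next sentence says that calculated loss cannot be determined in these women.

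Death appears only among the secondary outcomes, as "incidence of maternal death from any cause". Under Statistical methods and data reporting, the main analysis uses a modified ITT population of randomised women who have a caesarean, apart from withdrawals of consent and women found ineligible. No rule is given for a missing primary outcome.

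**The concern.** **D3 haematocrit after transfusion.** As punctuated, the no-transfusion condition governs only the last fallback. Take a woman with no D2 sample who receives red cells after D2 and is then sampled on D3. She is not an event by transfusion, because that window closed at D2. Her D3 value, raised by donor cells, goes into the formula. The plan accepts that transfusion makes the calculation unusable, but applies this only to women transfused by D2.

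**The same route at D2.** The section Primary Outcome counts any red-cell transfusion, while Primary outcome measure counts only one given for PPH. Under the second wording, a transfusion before D2 recorded for another reason is not an event, yet it can raise the D2 haematocrit.

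**Death before sampling.** A woman who dies of haemorrhage without red cells and before any postoperative haematocrit meets neither route. She stays in the modified ITT population with a missing outcome. If only an early postpartum sample exists, the last fallback uses that.

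The stake is events lost from an endpoint planned on few events. The trial is open-label and the researchers analyse it with the statistician, so a case without a rule may be settled by people who know the arm.

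**Working it through.** **Planned size (Sample size section).** Inputs: 2.1% and 5.8%, two-sided alpha 0.05, power 90%, 1:1 allocation. Fleiss formula:

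n = [1.96·√(2 × 0.0395 × 0.9605) + z·√(0.021 × 0.979 + 0.058 × 0.942)]² / 0.037²

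With the unrounded normal quantile for 90% power, n = 581 per group and 1,162 in total, as stated (the printed 1.28 gives 580). Power at 581 per group is 90.0%. Expected events are 581 × 0.021 = 12.2 and 581 × 0.058 = 33.7, about 46 together. No planning figure is in dispute.

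**Loss hidden by a transfusion before the sample.** Assumed, since the documents give no such values: 70 kg, preoperative haematocrit 36%, one unit raising haematocrit by 3 points (range 2 to 4).

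- Blood volume: 70 × 85 = 5,950 mL.
- Fall needed for 1000 mL: 36 × 1000 / 5,950 = 6.05 points.
- Hidden by one unit: 5,950 × 3 / 36 = 496 mL (2 points: 331; 4 points: 661).
- Largest true loss scored as no PPH after one unit: 1,496 mL (1,331 to 1,661).
- Hidden by two units: 992 mL (661 to 1,322).
- Over 60 to 80 kg and preoperative haematocrit 30 to 36%, one unit hides 283 to 907 mL.

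Example near the threshold: a fall from 36% to 28.5% gives 5,950 × 7.5 / 36 = 1,240 mL, which is PPH. Raised by 3 points to 31.5%, it gives 5,950 × 4.5 / 36 = 744 mL, which is not.

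Example of a large loss: a fall to 22% gives 5,950 × 14 / 36 = 2,314 mL. After one unit it scores 5,950 × 11 / 36 = 1,818 mL, and after two 5,950 × 8 / 36 = 1,322 mL. It remains PPH.

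**Effect on the comparison.** If the same fraction f of events in each arm is scored as non-events, the relative risk is 0.021(1 − f) / [0.058(1 − f)] = 0.362, unchanged. If 5% of events are instead excluded from each arm:

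- TXA: 0.01995 / 0.99895 = 0.01997
- Control: 0.0551 / 0.9971 = 0.05526
- Relative risk 0.361; risk difference 3.5 points instead of 3.7

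Power at 581 per group if events are scored as non-events (illustrations, not forecasts):

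| Events lost of 46 | Lost in proportion across arms | All lost from control |
|---|---|---|
| 1 | 89.4% | 87.8% |
| 3 | 87.9% | 82.1% |
| 5 | 86.3% | 74.8% |

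**The case against.** The D3 case needs several things together: no D2 sample, no qualifying transfusion by D2, red cells between D2 and the D3 sample, and a loss not far above 1000 mL. The plan recognises the transfusion problem, so the condition may simply be misplaced. Death, emergency surgery, shock and ICU transfer are reported as secondary outcomes, so a haemorrhage death would be visible. All this stands and limits the size of the problem, but the written rule still gives the wrong score when followed.

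Three stronger readings are tempting and are not supported.

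- *The rules misclassify the most severe bleeders.* Women transfused for PPH by D2 are events automatically, and very large losses can still exceed the threshold after a unit or two, as shown above. The D3 rule mainly affects late-transfused women near the threshold. The death case is a missing outcome; it becomes misclassification only if blanks are counted as non-events.
- *The error shrinks the measured effect.* The plan reports both relative risks and risk differences. Equal fractional loss reduces the risk difference but leaves the relative risk almost unchanged. Attenuating the relative risk needs a larger fraction lost in control, and nothing in the documents shows that.
- *National mortality sizes the death problem.* The Introduction's 651 per 100,000 and 21–43% due to PPH would give 1,162 × 0.00651 × 0.21 = 1.6 to 1,162 × 0.00651 × 0.43 = 3.3 deaths. That applies an all-births rate to women selected by exclusions such as praevia, abruption and eclampsia. It also counts all PPH deaths rather than the untransfused, unsampled ones. The Justification says that obstetric patients receive blood products at no cost. The affected number could be zero.

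The comparison with 46 events also depends on the planning rates. At the pilot's per-protocol 22.6% and 31.4%, 581 per group would give 581 × 0.540 = about 314 events, and one lost event would hardly matter.

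**Conclusion.** The point holds as a gap in the primary-outcome definition. Following the written D3 rule can score a true PPH as a non-event, and the differing transfusion wordings open the same route at D2. Haemorrhage death without transfusion or a haematocrit has no assigned outcome. The number of women is unknown from the documents and probably small. The masked volume rests on the assumed weight, haematocrit and rise per unit. The likely consequence is a modest loss of events, risk difference and power; a material effect on the relative risk would require losses that differ by arm. The change is worth making because it costs little and settles severe or awkward cases before the arm is known.

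**What to change.** 1. State that no haematocrit taken after a red-cell transfusion is used for calculated blood loss, whether at D2, at D3 or under any fallback. If D2 is missing and red cells were given before the D3 sample, use the latest postpartum haematocrit taken before transfusion. Add a sensitivity analysis that counts these women as PPH.
2. Use one wording of the transfusion criterion in Primary Outcome and in Primary outcome measure.
3. State that death from haemorrhage between delivery and D2 counts as PPH whether or not a haematocrit exists.

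Emergency surgery should not be added to the primary outcome. No defect is shown for it, since survivors can still qualify by haematocrit or transfusion, and it would put a clinician-decided component into an open-label endpoint that was chosen for its objectivity.

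The cost is a few sentences, using samples, transfusion records and deaths already collected; the planned 1,162 does not change at the assumed rates. There are two downsides. The definition departs slightly from that of the source trial. The pre-transfusion sample may also be an early one, or may not exist, which is why the sensitivity analysis is needed.

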 - iii. sensation of rings or spots of light in visual field
 - iv. dizziness
- c. the occurrence of potential severe adverse effects of TXA during the hospital stay and up to discharge
 - i. deep vein thrombosis, if the diagnosis is confirmed by Doppler ultrasound
 - ii. pulmonary embolism, if the diagnosis is confirmed by radiological examination
 - iii. myocardial infarction
 - iv. seizure
 - v. renal failure requiring dialysis
- d. any other unexpected adverse events

Data Management

The researcher and assistants will allocate each patient codes. No identifiers will be used. Any data collected will be stored in an office accessible only to the researcher and research assistants, as well as on a password-protected laptop computer.

data cleaning and entry

Completed questionnaires will be checked for validity, accuracy and completeness by the principal investigator before data entry into the computer.

Statistical methods and data reporting

Data analysis and reporting will be guided by the Consolidated Standards of Reporting Trials (CONSORT) and will be done by the researchers with the assistance of the statistician. (34).

The women's demographic characteristics and standard risk factors for PPH will be compared between the two groups.

The main analysis of the primary and secondary outcomes will be performed in the modified intention-to-treat (ITT) population, defined as women who undergo randomization and have a caesarean delivery (except if they withdraw consent or are deemed ineligible after randomization).

We will also analyse two separate per-protocol populations: women from the modified ITT population receiving a uterotonic and TXA (as specified in the protocol) (per-protocol group 1); the other will include women from the modified ITT population receiving a uterotonic and then tranexamic acid or no TXA in the 10min after delivery (per-protocol group 2; for a situation more consistent with routine clinical practice). The baseline characteristics of the trial participants, the management of the third stage of labour, and protocol adherence will be compared by descriptive statistics.

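### The calculated-loss part of the primary (>1000 mL without transfusion) has no output of its own, and women transfused for PPH drop out of the calculated-loss secondary outcomes

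*Combined protocol and SAP*

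**What the plan says.** The trial is open label (Research design), and the surgical team manages PPH under local guidelines (Other aspects of the caesarean delivery).

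The primary outcome combines calculated loss above 1000 mL with red-cell transfusion up to day 2 (D2). Under Primary outcome measure: "All women who receive RBC transfusion for PPH between delivery and D2 postpartum are defined to have PPH". Three reasons follow. The first is "Calculated blood loss is impossible to determine for these women". The second is that "women only rarely receive an RBC transfusion for a blood loss less than 1000 ml". The third is that transfusion is at least as serious a marker of morbidity as a loss above 1000 mL.

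Under Secondary outcome measures, Laboratory, the plan lists:
- item a: "incidence of calculated blood loss > 500 mL and > 1500 mL";
- item b: "mean total calculated blood loss";
- item c: "mean peripartum change in haemoglobin (difference between haemoglobin before delivery and at D2");
- item d: a haemoglobin drop of more than 2 g/dL over the same interval.

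The clinical list adds the incidence of postpartum transfusion, without limiting it to D2 or to PPH.

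Statistical methods and data reporting states: "The main analysis of the primary and secondary outcomes will be performed in the modified intention-to-treat (ITT) population". The haematocrit rule mentions transfusion once, for the case where both the D2 and D3 values are missing: "then the postpartum haematocrit closest to D2 in the absence of transfusion will be considered".

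**The concern.** Two things are missing.

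First, the plan reports thresholds on either side of 1000 mL but not 1000 mL itself. The haematocrit-based part of the primary is the part least open to the judgement of staff who may know the arm. That their PPH management includes the decision to transfuse is an inference, although a natural one. If the primary differs between arms, a reader will want to know whether the difference lies in measured loss, in transfusion, or in both. The listed outputs answer this only in part.

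Second, calculated loss is declared undeterminable in women transfused for PPH, yet items a and b are to be analysed in the whole modified ITT population. Taken literally, these women have no value and leave the analysis. They are likely to be among the heaviest bleeders, and if TXA works there should be more of them in the control arm. Exclusion after randomisation on that basis can hide a benefit. Counting all of them above a high threshold can exaggerate one. Items c and d have the reverse problem: the D2 haemoglobin is used as it stands, although a transfusion before it can mask the fall.

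**Working it through.** **Plan's own figure.** With p1 = 0.021, p2 = 0.058, mean 0.0395, two-sided 5% and 90% power, the printed formula is

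n = [1.96 √(2 × 0.0395 × 0.9605) + 1.28 √(0.021 × 0.979 + 0.058 × 0.942)]² / 0.037² = 579.8.

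With unrounded normal quantiles it gives 580.3, rounded up to 581 per arm. The stated 581 is reproduced, and nothing below changes it.

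**Inputs for the illustrations.** All use 581 per arm. The documents give no component rates for this composite, so the transfusion rates are borrowed from the nine-trial caesarean meta-analysis in the Literature review: 1.9% versus 5.7%. This gives 581 × 0.019 = 11.0 and 581 × 0.057 = 33.1, that is 11 versus 33 transfused women, leaving 570 versus 548. This is an assumption and does not estimate what this trial will see.

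**Why the component table matters.** At the plan's primary rates, 581 × 0.021 = 12.2 and 581 × 0.058 = 33.7 events are expected. Set beside 11 and 33 transfusions, nearly all primary events could be transfusions. At the pilot's per-protocol rates (22.6% versus 31.4%), 131 versus 182 events are expected. Then 131 − 11 = 120 and 182 − 33 = 149 come from calculated loss alone, so most events are of that kind. The plan's own sources allow either picture.

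**>1000 mL, pilot rates.**
- Transfused women counted as cases: 131/581 versus 182/581, RR 0.72, identical to the primary.
- Transfused women left out: 120/570 versus 149/548, RR 0.77.

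The two versions agree in direction and broadly in size.

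**>1500 mL.** Assume the same true rate in non-transfused women of both arms, with counts rounded to whole women. P-values are Fisher's exact, before the Benjamini–Hochberg step.

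| Rate in non-transfused | Transfused left out | RR | All transfused counted | RR | p |
|---|---|---|---|---|---|
| 2% | 11/570 vs 11/548 | 0.96 | 22/581 vs 44/581 | 0.50 | 0.007 |
| 3% | 17/570 vs 16/548 | 1.02 | 28/581 vs 49/581 | 0.57 | 0.018 |
| 5% | 28/570 vs 27/548 | 1.00 | 39/581 vs 60/581 | 0.65 | 0.035 |
| 10% | 57/570 vs 55/548 | 1.00 | 68/581 vs 88/581 | 0.77 | 0.10 |

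The left-out versions all have p = 1.0. Uncorrected chi-square on the all-counted tables gives 0.005, 0.013, 0.027 and 0.085, so the reading does not depend on the test. Counting every transfused woman above 1500 mL is an upper limit; the plan's argument supports only >1000 mL.

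**Mean loss.** Assume 600 mL in non-transfused women of both arms and 1500 to 2500 mL in transfused women; none of these values is in the documents. Leaving the transfused out hides (33 − 11)/581 × (1500 − 600) = 34 mL to (33 − 11)/581 × (2500 − 600) = 72 mL. Against the 160.27 mL difference in the same meta-analysis, that is 21% to 45%.

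**The case against.** The best reply is that the gap is narrow. The composite is argued for and counts transfused women explicitly. The calculated-loss part can be recovered by subtracting women transfused for PPH by D2 from the primary cases, using data the primary already needs. The statement that transfusion is at least equivalent to a loss above 1000 mL implies that these women are >500 mL and >1000 mL cases. The sentence declaring their loss undeterminable tells against computing one from a post-transfusion haematocrit. Items c and d do name the value to be used.

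Most of this stands, and it makes the point minor. What remains is that the subtraction is not planned, and the listed transfusion outcome cannot stand in for it because it is not restricted to D2 or to PPH. The equivalence argument is never carried over to item a. It also says nothing about >1500 mL or the mean. Naming the D2 haemoglobin does not remove the effect of a transfusion given before it.

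A reader might go further and infer that a few discretionary transfusions in controls would overturn the primary result. Moving the planned 12 versus 34 events to 12 versus 24 gives p = 0.061 by Fisher's test but 0.042 by chi-square, which the plan also allows. It also requires ten sub-1000 mL transfusions in controls and none on TXA. Nothing in the documents suggests such an imbalance, and the plan describes transfusion at such losses as rare.

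A reader might also infer that the counting rule decides significance at >1000 mL. That needs transfused women to be counted as non-cases (120/581 versus 149/581; p = 0.051 by Fisher, 0.044 by chi-square). This contradicts the plan's own equivalence argument and again depends on the test.

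**Conclusion.** The concern holds as a minor one, limited to the secondary outcomes and to interpretation of the primary. The composite, its analysis and the 581 per arm stand. The >1000 mL part of the primary is not shown on its own. As written, women transfused for PPH fall out of items a and b, while items c and d use a haemoglobin value that transfusion can raise.

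The size and direction of any bias cannot be known from the documents. The clearest illustration is >1500 mL: RR about 1.0 with transfused women left out against 0.50 to 0.65 with all counted, at background rates of 2% to 5%, fading to 0.77 (p = 0.10) at 10%. It rests on borrowed transfusion rates, on no effect in non-transfused women, and on an upper-limit counting rule. It shows that the rule matters enough to be fixed before the data are seen. It does not show that the trial's conclusions would be wrong, and open-label conduct alone does not show that transfusion decisions will differ by arm.

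**What to change.** Keep the composite primary and every listed secondary outcome, and make these changes:

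1. In laboratory item a, add >1000 mL between the two existing thresholds. Tabulate the primary by arm in three rows: transfused for PPH by D2; not transfused with calculated loss >1000 mL; neither.
2. For >500 mL and >1000 mL, count women transfused for PPH as cases, with a sensitivity version that excludes them. Counting them at >1000 mL reproduces the primary, so the excluding version and the table carry the new information.
3. For >1500 mL, show both limits: none of the transfused women counted, and all counted.
4. Beside mean calculated loss, give the number of women per arm without a value.
5. For items c and d, add a version that does not use haemoglobin measured after a transfusion, with the number of women affected per arm.

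A further analysis using pre-transfusion haematocrit is not recommended, because an early value can understate loss.

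The cost is some SAP wording and a few extra table rows. There is no new blood test and no change to care, sample size or the primary analysis.
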